15.4.2. Treatment Emergent Flag for Adverse Events

Flag	Definition
Treatment Emergent	
• Study Treatment Start Date \leq AE Start Date• AE Start Date is missing

NOTES:

- If the study treatment stop date is missing, then the AE will be considered to be On-Treatment.
- Time of study treatment dosing and start/stop time of AEs should be considered, if collected.

15.5. Appendix 5: Data Display Standards & Handling Conventions

15.5.1. Reporting Process

Software	

 The currently supported versions of SAS software will be used. 	
Reporting Area	
HARP Server	: US1SALX00259
HARP Compound	: arprod\gsk2859716\MID205678\
Analysis Datasets	

 Analysis datasets will be created according to CDISC standards (SDTM IG Version 3.2 & ADaM IG Version 1.1). 	
Generation of RTF Files	
RTF files will be generated for all tables.	

15.5.2. Reporting Standards

General	

 The current GSK Integrated Data Standards Library (IDSL) will be applied for reporting, unless otherwise stated (IDSL Standards Location: https://spope.gsk.com/sites/IDSLLibrary/SitePages/Home.aspx): 
 4.03 to 4.23: General Principles 5.01 to 5.08: Principles Related to Data Listings 6.01 to 6.11: Principles Related to Summary Tables 7.01 to 7.13: Principles Related to Graphics Do not include subject level listings in the main body of the GSK Clinical Study Report. All subject level listings should be located in the modular appendices as ICH or non-ICH listings 	
Formats	

 GSK IDSL Statistical Principles (5.03 & 6.06.3) for decimal places (DP's) will be adopted for reporting of data based on the raw data collected, unless otherwise stated. Numeric data will be reported at the precision collected on the eCRF. The reported precision from non eCRF sources will follow the IDSL statistical principles but may be adjusted to a clinically interpretable number of DP's. 	
Planned and Actual Time	

 Reporting for tables, figures and formal statistical analyses: 
 Planned time relative to dosing will be used in figures, summaries, statistical analyses and calculation of any derived parameters, unless otherwise stated. The impact of any major deviation from the planned assessment times and/or scheduled visit days on the analyses and interpretation of the results will be assessed as appropriate. Reporting for Data Listings: 
 Planned and actual time relative to study drug dosing will be shown in listings (Refer to IDSL Statistical Principle 5.05.1). Unscheduled or unplanned readings will be presented within the subject's listings. 	
Unscheduled Visits	

 Unscheduled visits will not be included in summary tables and/or figures. 
 For by planned time analysis, unscheduled visits will not be included; For worst-case analysis, unscheduled visits will be included. 	

 All unscheduled visits will be included in listings. 	
Descriptive Summary Statistics	
Continuous Data	Refer to IDSL Statistical Principle 6.06.1
Categorical Data	N, n, frequency, %
Graphical Displays	

 Refer to IDSL Statistical Principals 7.01 to 7.13. 	

15.5.3. Reporting Standards for Pharmacokinetic

Pharmacokinetic Concentration Data	
PC Windows Non-Linear (WNL) File	PC WNL file (CSV format) for the non-compartmental analysis by Clinical Pharmacology Modelling and Simulation function will be created according to SOP 00000314000: Non-Compartmental Analysis of Clinical Pharmacokinetic Data. Note: Concentration values will be imputed as per GUI_51487
Descriptive Summary Statistics, Graphical Displays and Listings	Refer to IDSL PK Display Standards. Refer to IDSL Statistical Principle 6.06.1. Note: Concentration values will be imputed as per GUI_51487 for descriptive summary statistics/analysis and summarized graphical displays only.
NONMEM/Pop PK File	See separate population PK/exposure-response analysis RAP
NONMEM/PK/PD File	See separate population PK/exposure-response analysis RAP
Pharmacokinetic Parameter Derivation	
PK Parameter to be Derived by Programmer	The following PK parameters will be derived by the Programmer: 
 C-EOI and Ctrough for cycles with predose and EOI sampling only Accumulation ratios based on Cycle 1 and Cycle 3 AUC and Cmax values
Pharmacokinetic Parameter Data	
Is NQ impacted PK Parameters Rule Being Followed	Yes, refer to [Standards for Handling NQ Impacted PK Parameters].
Descriptive Summary Statistics, Graphical Displays and Listings	Refer to IDSL PK Display Standards.

15.5.4. Extended Loss to Follow-up or Extended Time without an Adequate Assessment

For subjects, if two or more scheduled disease assessments are missed and are then followed by an assessment of PD or death, PFS will be censored at the last adequate assessment prior to PD or death. When the scheduled disease assessment is every 3 weeks, a window of 49 days (6 weeks + 7 day window) will be used to determine whether there was an extended time without adequate assessment. That is, if the time difference between PD/death and last adequate assessment is more than 49 days, then PFS will be censored at the last adequate assessment prior to PD/death.

15.6. Appendix 6: Derived and Transformed Data

15.6.1. General

Multiple Measurements at One Analysis Time Point

 • Mean of the measurements will be calculated and used in any derivation of summary statistics but if listed, all data will be presented. • Participants having both High and Low values for Normal Ranges at any post-baseline visit for safety parameters will be counted in both the High and Low categories of “Any visit post-baseline” row of related summary tables. This will also be applicable to relevant Potential Clinical Importance summary tables.
Study Day

 • Calculated as the number of days from First Dose Date: 
 • Ref Date = Missing → Study Day = Missing • Ref Date < First Dose Date → Study Day = Ref Date – First Dose Date • Ref Date ≥ First Dose Date → Study Day = Ref Date – (First Dose Date) + 1

15.6.2. Study Population

Extent of Exposure

 • Number of days of exposure to study drug will be calculated based on the formula: Duration of Exposure in Days = min(Last infusionDate+20, Death date) – First infusion Date + 1 • Participants who were randomized but did not report a treatment start date will be categorised as having zero days of exposure. • The cumulative dose will be based on the formula: Cumulative Dose (mg/kg) = Sum of Dose at Each Cycle • Dose intensity will be calculated based on the formula: • Dose intensity (mg/kg/3 week) = Cumulative Dose/((last infusion date – first infusion date + 21)/21)

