6.5. Extent of Exposure

Extent of exposure to GSK2857916 will be summarized.

The number of cycles administered to study treatment will be summarised with mean, median, standard deviation, minimum, and maximum.

Dose delivered per cycle (mg/kg/cycle) will be summarized using mean, median, standard deviation, minimum, and maximum by cycle and overall. The dose intensity (mg/kg/3 weeks), which is calculated as the cumulative actual dose (mg/kg) divided by expected duration of exposure in 3 weeks (last infusion date – first infusion date +

21)/21), will also be summarized. A by subject summary listing of data on exposure to all study treatments will be produced.

Dose reductions will be summarised by number of reductions and reasons for reductions. Dose delays will be summarised by number of delays, reasons for the delays, and delay duration (days). The number and percentage of the delays for intervals of 1-21, 22-42 and >42 days will be computed. Primary reasons for dose reductions and dose delays will also be summarized by cycle. Listing of all dose delays due to corneal events (GSK scale) and listing of dose delays and associated Eye Disorder Events (CTCAE) will be produced.

Duration of delays is defined as period from the expected start date of dose to actual start date of current dose. Calculation: (actual start date of current dose - expected start date of dose). Expected start date of dose = actual start date of previous dose + 21.

The summaries of dose modifications will be provided. All the dose reductions, dose escalations, infusion interruptions, incomplete infusions and dose delays will be listed. A plot showing the number and percentage of subjects treated at different dose levels over time will be provided.

The duration of exposure to study treatment (from first day to last day of treatment) will be calculated and summarized using mean, median, standard deviation, minimum, and maximum. A horizontal bar graph of duration of treatment will be produced that displays duration of treatment in months for each subject. Summary of duration of exposure by response category based on IRC will be presented.

A Kaplan Meier curve for time to treatment discontinuation by Response Category Based on IRC, and a Kaplan Meier curve for time to treatment discontinuation for subjects who have received at least 3 cycles of the study treatment will be presented.

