6.6. Concomitant Medications

Concomitant medications will be coded using GSK Drug coding dictionary, summarized, and listed. The summary of concomitant medications will show the number and percentage of subjects taking concomitant medications by Ingredient. Multi-ingredient products will be summarized by their separate ingredients rather than as a combination of ingredients. Anatomical Therapeutic Chemical (ATC) classification Level 1 (Body System) information will be included in the dataset created but will not appear on the listing or summary.

In the summary of concomitant medications, each subject is counted once within each unique ingredient. For example, if a subject takes Amoxicillin on two separate occasions, the subject is counted only once under the ingredient "Amoxicillin". In the summary of concomitant medications, the ingredients will be summarized by the base only, using CMBASECD and CMBASE. Note: In order to be considered a concomitant medication, the concomitant medication must have been taken at some point during the on-treatment window.

Prophylactic medication for infusion-related reactions and prophylactic topical eye medications will be summarized by drug class and drug name and listed separately. In addition, the percentage of duration of exposure (see Section 15.6.2 for definition) that was on prophylactic steroid eye drop use will also be summarized.

Blood products or blood supportive care products with onset date within the on-treatment window will be included in the summary tables. The frequency and percentage of subjects using blood products and blood supportive care products after the start of study medication will be provided. Supporting listings will also be provided.

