8.2.3. Corneal events (GSK scale)

Following discussions with regulatory agencies, GSK developed a grading scale to capture both corneal examination findings and visual acuity changes in participants treated with GSK2857916. This GSK scale differs from the CTCAE criteria for eye disorders which relies mainly on patient's symptoms and patient's ability to attend to 'activities of daily living' for grading of events. Details of derivation this GSK scale based on corneal findings and visual acuity Ophthalmic Exam (collected from Ocular

form) can be found in Appendix 9 Table 22 and Table 23 of study protocol (Version: GSK Document Number [TMF-13990464](#)).

In addition to the listing, the following outputs will be provided for corneal events graded using the GSK scale:

1. Overview for corneal event (GSK scale)
2. Summary of grade of GSK scale
 - a. Summary of characteristics of corneal events (GSK scale) including the percentage of duration of exposure (see Section 15.6.2 for definition) with corneal events (GSK scale) of grade ≥ 2 and grade ≥ 3 respectively
 - b. Summary of onset time and duration of the first occurrence of corneal event (GSK scale) of a) grade 2 or above; 2) grade 3 or above.
3. Summary of actions taken with study treatment (e.g. dose reduction/delay/permanent discontinuation)
4. Summary of time to re-initiation of study treatment post treatment delay due to corneal events (GSK scale)
5. Change in grade of corneal events (GSK scale) from EOT to last follow-up
6. Summary of worst post-baseline corneal events (GSK scale)
7. Summary of worst post-baseline corneal events (GSK scale) by best response (PR or better vs. otherwise)
8. Summary of resolution (improve to grade 1 or better) in corneal events (GSK scale) during Follow-up period (from EOT visit to last follow-up visit).
9. Logistic regression analysis will be performed to explore possible risk factors for developing corneal Events (GSK scale ≥ 2). In addition to dose arm (3.4 mg/kg vs 2.5 mg/kg), Sex (Male vs Female), Age Group (< 65 vs. ≥ 65 years), Race (White, Other), the following risk factors will also be considered:
 - a. History of intraocular surgery: (Yes vs. No)
 - b. Lens status (pseudophakia vs natural lens) at baseline
 - c. Known history of dry eye per screening questionnaire (Presence vs. Absence)
 - d. Presence of keratopathy at baseline exam (None vs. Mild vs. Moderate/Severe)

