	
end dates are not imputed, with the following exceptions for imputation of missing treatment end date at interim analyses.
 
 • For imputation of missing exposure end date at an interim analysis when subjects are still on treatment, the following conventions will be applied: 
 ○ If the missing end date is in the last exposure record, the earliest of: the date of the data cut-off, the date of withdrawal from the study, or the death date will be used ○ If the missing end date is not in the last exposure record, treatment start date for the record will be used • The imputed treatment end date will be used to calculate cumulative dose and duration of treatment as specified in Section 15.6.2 
If treatment end date is missing for a cycle, treatment start date for the cycle will be used.

PACT	
 • For PACT subjects, subject's last Visit date will be used as subject's end of study date, wherever required.

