15.14. Appendix 14: Example Mock Shells for Data Displays

Example POP_T1
 Protocol: 205678
 Population: Safety

Page 1 of 1
 (Data as of: 24APR2018)

Table X
 Summary of Percentage of Duration of Exposure on Steroid Eye Drop

	Treatment Group A (N=100)	Treatment Group B (N=100)
% of duration of exposure [1] that was on Prophylactic steroid eye drop		
n	100	100
Mean	20.5	15.1
SD	1.44	1.24
Median	18	14
Min.	3	1
Max.	40	30

Note:

1: Duration of Exposure in Days is calculated as minimum of (Treatment Stop Date+21, Death date) minus Treatment Start Date.

Example EFF_T1

Protocol: 205678

Population: ITT

Page 1 of 1

Table X.X
Summary of MRD Negativity Rate by Best Response

			Treatment Group A (N=xx)	Treatment Group B (N=xx)
Best response				
Stringent Complete Response (sCR)	n		xx	xx
	MRD Negativity Rate		xx (xx.x%)	xx (xx.x%)
	95% Confidence Interval		(xx.x%, xx.x%)	(xx.x%, xx.x%)
Complete Response (CR)	n		xx	Xx
	MRD Negativity Rate		xx (xx.x%)	xx (xx.x%)
	95% Confidence Interval		(xx.x%, xx.x%)	(xx.x%, xx.x%)
Very Good Partial Response (VGPR)	n		xx	xx
	MRD Negativity Rate		xx (xx.x%)	xx (xx.x%)
	95% Confidence Interval		(xx.x%, xx.x%)	(xx.x%, xx.x%)
sCR/CR/VGPR	n		xx	xx
	MRD Negativity Rate		xx (xx.x%)	xx (xx.x%)
	95% Confidence Interval		(xx.x%, xx.x%)	(xx.x%, xx.x%)

Note: Minimal Residual Disease (MRD) negativity rate is defined as: the percentage of participants who are MRD negative by Next Generation Sequencing (NGS).

Example EFF_T2
 Protocol: 205678
 Population: Full Analysis

Table X.X
 Summary of Reasons of Censoring

Time to event endpoints		Treatment Group A (N=xx)	Treatment Group B (N=xx)
Duration of response(DoR)	n	xx	xx
	Reason 1	xx (xx.x%)	xx (xx.x%)
	Reason 2	xx (xx.x%)	xx (xx.x%)
	Reason 3	xx (xx.x%)	xx (xx.x%)
		
Progression free survival(PFS)	n	xx	xx
	Reason 1	xx (xx.x%)	xx (xx.x%)
	Reason 2	xx (xx.x%)	xx (xx.x%)
	Reason 3	xx (xx.x%)	xx (xx.x%)
		
Time to progression(TTP)	n	xx	xx
	Reason 1	xx (xx.x%)	xx (xx.x%)
	Reason 2	xx (xx.x%)	xx (xx.x%)
	Reason 3	xx (xx.x%)	xx (xx.x%)
		
Overall survival(OS)	n	xx	xx
	Reason 1	xx (xx.x%)	xx (xx.x%)
	Reason 2	xx (xx.x%)	xx (xx.x%)
	Reason 3	xx (xx.x%)	xx (xx.x%)
		

n is the number of subject who were censored, which will be used as denominator to calculate the percentage.

Example SAFE_T11
Protocol: 205678
Population: Full Safety

Table X.X
Summary of Thrombocytopenia and Bleeding Event

	Treatment	Treatment	Treatment
	Group A	Group B	Group C
	(N=100)	(N=100)	(N=100)

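### The duration-of-exposure formula in SAP 15.6.2 has no data cut-off term, so participants infused fewer than 20 days before cut-off are credited with up to 20 days that have not elapsed, which distorts their percent-of-exposure figures

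*SAP*

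**What the plan says.** Three places in the SAP describe duration of exposure.

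- Section 15.6.2 (Extent of Exposure): "Duration of Exposure in Days = min(Last infusionDate+20, Death date", from which the first infusion date is subtracted and 1 is added.
- Section 6.5: "The duration of exposure to study treatment (from first day to last day of treatment) will be calculated". This is a description with neither a 20-day extension nor a death term.
- Appendix 14, footnote to mock shell POP_T1 (the shell for Table 1.0170): "Duration of Exposure in Days is calculated as minimum of (Treatment Stop Date+21, Death date) minus Treatment Start Date".

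Section 15.6.2 governs. Section 6.6 refers to it for "the percentage of duration of exposure (see Section 15.6.2 for definition) that was on prophylactic steroid eye drop use", and Section 8.2.3 refers to it for the "percentage of duration of exposure (see Section 15.6.2 for definition) with corneal events (GSK scale) of grade" 2 or above and 3 or above.

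A cut-off rule does exist in Section 15.7.2.1. It applies at an interim analysis when the exposure end date is missing: "If the missing end date is in the last exposure record, the earliest of: the date of the data cut-off", the date of study withdrawal or the death date. The section adds: "The imputed treatment end date will be used to calculate cumulative dose and duration of treatment as specified in Section 15.6.2".

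**The concern.** The 15.6.2 formula treats each infusion as covering 21 days. For a participant who has stopped treatment, all of that time has passed by the analysis. For a participant still being dosed, part of it lies after the cut-off, where no event, eye-drop use or death can yet be in the data.

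Two kinds of output are touched. The duration summaries (Tables 1.0260 and 1.11140) contain days not yet observed. The percentage tables (1.0170 for steroid eye drops, 3.1320-3.1324 for CTCAE eye events, 3.1330-3.1331 for corneal events on the GSK scale) divide by those days. Eye disorder and corneal events are adverse events of special interest in this trial, and these tables state how much of treated time participants spent with them. Shell SAFE_T22 also sorts the percentages into 20-point bands, so a participant near a band edge can change band.

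**Working it through.** **Notation.** F is the first infusion date, L the last infusion date, D the death date and K the data cut-off date. Day offsets are counted from F = 0.

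- A = min(L + 20, D) - F + 1 (Section 15.6.2)
- B = min(L + 21, D) - F (POP_T1, taking the stop date as the last infusion date)
- C = L - F + 1 (Section 6.5 read literally, with the last day of treatment taken as the last infusion)
- A with cut-off = min(L + 20, D, K) - F + 1

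**Step 1: the three wordings, participant alive.**

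| L (offset) | A | B | C |
|---|---|---|---|
| 0 | 21 | 21 | 1 |
| 21 | 42 | 42 | 22 |
| 63 | 84 | 84 | 64 |
| 168 | 189 | 189 | 169 |

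A and B are identical here. They differ by one day (A = B + 1) only when death falls 0 to 20 days after the last infusion, because B then omits the final + 1. C is 20 days shorter than A.

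**Step 2: days credited beyond cut-off.** For a living participant the excess is L + 20 - K when positive. That is 20 days for an infusion on the cut-off day, falling to 0 for one given 20 days earlier. With L spread evenly over 0 to 20 days before cut-off (an assumption), the mean excess is 10 days.

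- K = 183, L = 183: A = 183 + 20 + 1 = 204; elapsed = 183 + 1 = 184.
- K = 183, L = 143 (a 40-day gap): A = 143 + 20 + 1 = 164, below the 184 elapsed. No unelapsed time is credited.

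The 183 days stands for the 6 months between the last frozen-liquid randomization and the primary analysis (SAP Section 3.2), taking first infusion as close to randomization.

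**Step 3: effect on a true 50%, numerator stopped at cut-off.** At worst the multiplier is (K + 1)/(K + 21).

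| K (days) | Worst-case multiplier | 50% at worst | 50% on average |
|---|---|---|---|
| 85 | 86/106 = 0.811 | 40.6% | 45.0% |
| 183 | 184/204 = 0.902 | 45.1% | 47.5% |
| 365 | 366/386 = 0.948 | 47.4% | 48.7% |

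**Step 4: the direction depends on the numerator.** Take an event starting at offset 91 and ongoing at K = 183, with L = 183.

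- Both parts ended at cut-off: (183 - 91 + 1)/184 = 93/184 = 50.5%.
- Numerator stopped at cut-off, denominator as in 15.6.2: 93/204 = 45.6%.
- Numerator carried to the end of credited exposure (offset 203): 113/204 = 55.4%.

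**Step 5: does Section 15.7.2.1 cure it?** No. It is confined to interim analyses and missing end dates, and it sends a treatment end date to a formula that has no such term. If the imputed cut-off date is used in place of the last infusion date, the formula still adds 20 days: 204 against 184.

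**The case against.** The strongest defence is that crediting 21 days per infusion is a coherent convention. The dose-intensity denominator and the footnotes of SAFE_T4a and SAFE_T21 count the same way. That stands for dose intensity, where each dose is set against the interval it is meant to cover. It does not carry over to a percentage of time with an event, where the denominator should be time in which the event could have been seen.

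Three stronger readings are tempting, and the SAP does not support them.

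- **That the SAP has three conflicting formulas.** The two actual formulas agree except for one day in deaths within 20 days of the last infusion. Section 6.5 conflicts only if its last day of treatment means the last infusion; the SAFE_T21 footnote puts the end of treatment exposure at last infusion + 20, so 6.5 can be read consistently. Sections 6.6 and 8.2.3 point to 15.6.2 in any case.
- **That the percentages come out too low.** No rule says how far an ongoing event or eye-drop use is counted, and step 4 shows that the error can go either way.
- **That the distortion is large.** A participant with three doses, the last given the day before cut-off, and an event present throughout would show 44/63 = 70% instead of 100%. With five doses it would be 86/105 = 82%. At the primary analysis a frozen-liquid participant still on treatment has about 183 days or more elapsed, so the worst multiplier is about 0.90. Only lyophilized participants enrolled later could have such short follow-up.

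It is also true that a long dose hold removes the problem, that the relative error shrinks as exposure lengthens, and that only descriptive summaries are involved.

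**Conclusion.** The point holds in a limited form. The governing formula credits unelapsed time to living participants infused fewer than 20 days before cut-off: 0 to 20 days each, 10 on average if last-infusion timing is uniform. At about 183 days the resulting relative error in a percentage is roughly 5% on average and 10% at most when the numerator stops at cut-off. If ongoing events are carried to the end of credited exposure, the figure may instead be too high.

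Participants 20 or more days past their last infusion are unaffected. The SAP does not give the share of participants affected, so the shift in the table-level summaries cannot be stated. ORR is untouched. The mismatched wording in Section 6.5 and POP_T1 is secondary: 20 days on a literal reading of the first, one day in certain deaths for the second. The correction is worth making because the rule as written gives a wrong denominator for the ocular-burden tables and is cheap to put right.

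**What to change.** 1. In Section 15.6.2, define exposure once as min(last infusion date + 20, death date, data cut-off date) - first infusion date + 1.
2. State that events and eye-drop use still ongoing are truncated in the numerator at that same end date. Without this, capping the denominator alone could produce percentages above 100%.
3. Replace the wording in Section 6.5 and the POP_T1 footnote with a cross-reference to 15.6.2.
4. Align the cross-reference in Section 15.7.2.1, so that an imputed end date is not extended by a further 20 days, and align the end-of-treatment-exposure footnote in SAFE_T21.

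The cost is a few sentences in the SAP and small changes to the exposure and percentage programs. Reported exposure for affected participants still on treatment falls by up to 20 days (204 to 184 in the example above). No data collection or design feature changes.
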